#### **5.1.2.4 Quality of Life (QOL) - EQ-5D-5L and EQ-5D-Y**

QOL will be evaluated using the EuroQol 5-Dimension 5 Level (EQ-5D-5L) for subjects  $\geq 18$  years of age and for subjects 12 to  $< 18$  years of age.

##### ***EQ-5D-5L***

The EQ-5D-5L consists of the EQ-5D-5L descriptive system and the EQ Visual Analogue scale (EQ VAS). The descriptive system comprises 5 dimensions: mobility, self care, usual activities, pain/discomfort, anxiety/depression. Each dimension has 5 levels: no problems, slight problems, moderate problems, severe problems, and extreme problems. The digits for 5 dimensions can be combined in a 5-digit number describing the respondent's health state.

EQ-5D-5L health states, defined by the EQ-5D-5L descriptive system, will be converted into a single index value. The index values, presented in country specific value sets, are a major feature of the EQ-5D instrument. EQ-5D-5L scoring will be based on EQ-5D-5L User Guide 2015 (UK Version 2, please refer to Appendix 2 for index score weights).

#### **5.1.3 Exploratory Efficacy Endpoint**

Intratumoral and peripheral blood anti-NY-ESO-1 immune changes biomarker analysis will be included in a Supplemental Statistical Analysis Plan (SSAP). This includes anti-NY-ESO-1 immune response and histologic and molecular changes in peripheral blood and tumor tissue and their association with clinical outcomes.

## **5.2 Safety Endpoints**

### **5.2.1 Adverse Events**

A treatment-emergent adverse event (TEAE) is defined as any AE that newly appeared or worsened in severity following initiation of the study treatment administration until 30 days after last dose of the study treatment. In addition, all study treatment related AEs are treated as TEAE.

Medical Event of Interest (MEOI) is defined as selected non-serious AEs are classified as MEOIs, refer to protocol section 6.4.7.5 for more details.

Immune-mediated event --

### **5.2.2 Clinical Laboratory Evaluations**

Clinical laboratory evaluations include hematology, serum chemistry, urinalysis, coagulation and viral tests.

**Hematology:** Hematocrit (HCT); hemoglobin (HGB); mean corpuscular hemoglobin (MCH); mean corpuscular hemoglobin concentration (MCHC); mean corpuscular volume (MCV); platelet count; red blood cell (RBC) count; white blood cell (WBC) count with differential; absolute neutrophil count (ANC); absolute lymphocyte count.

**Serum Chemistry:** Albumin; alkaline phosphatase; alanine aminotransferase (ALT); aspartate aminotransferase (AST); total protein; blood urea nitrogen (BUN); calcium; carbon dioxide; chloride; creatinine; creatinine clearance; uric acid; gamma-glutamyl transferase (GGT); glucose; lactate dehydrogenase (LDH); phosphorus; potassium; sodium; total bilirubin; direct bilirubin; thyroid stimulating hormone (TSH) (if TSH abnormal then T3, T4 to be evaluated).

**Urinalysis:** Appearance; bilirubin; color; glucose; ketones; microscopic examination of sediment; nitrite; occult blood; pH; protein; specific gravity; urobilinogen.

**Coagulation:** Prothrombin time (PT); partial thromboplastin time (PTT); international normalized ratio (INR).

**Viral Tests:** Hepatitis B (HepB), hepatitis C (HepC), or human immunodeficiency virus (HIV) infection.

### 5.2.3 Vital Signs

Vital Signs include body temperature, heart rate, respiratory rate, and resting systolic and diastolic blood pressure. On the day of each dosing, vital signs will be obtained before dosing and 30 minutes after dosing ( $\pm 10$  minute window). Blood pressure and heart rate will be measured no more than 60 minutes before the scheduled dosing.

### 5.2.4 Electrocardiogram (ECG)

ECG includes heart rate, PR interval, RR interval, QRS duration, QT interval, QTc interval and overall interpretation.

### 5.2.5 Other Safety Endpoints

ECOG, physical examination by body system, dosing and extent of exposure, prior and concomitant medication, and LV305 persistence will be also included to evaluate the safety of study treatment.

## 6 ANALYSIS SETS

Three analysis sets are considered in the statistical analysis of the study: Intent-to-Treat set (ITT), Efficacy Evaluable set (EE), and Safety set.

## 6.1 ITT Set

The ITT set consists of all subjects randomized. All analyses of this set will be based on the randomized treatment arm to which the subjects are assigned. Efficacy analyses performed in the ITT set will be considered to be the primary indicator of efficacy.

## 6.2 EE Set

The EE set consists of all subjects without major protocol violations, who have received at least 1 dose of study treatment, and have the baseline and at least 1 post-baseline tumor assessments available. The EE set will be analyzed according to the treatment received. Efficacy analyses performed in the EE set will be considered to be supportive.

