7.2 Analysis Sets

For the purpose of statistical analysis, there are 3 analysis sets: Intent-to-Treat set (ITT), Efficacy Evaluable set (EE), and Safety set.

- The ITT set consists of all subjects randomized. All analyses of this set will be based on the randomized treatment arm to which the subjects are assigned. Efficacy analyses performed in the ITT set will be considered to be the primary indicator of efficacy.
- The EE set consists of all subjects without major protocol violations, who have received at least 1 dose of study drug, and have the baseline and at least 1 post-baseline tumor assessments available. The EE set will be analyzed according to the treatment received. Efficacy analyses performed in the EE set will be considered to be supportive.
- The Safety set consists of all subjects taking any amount of study drug. The Safety set is the primary set for safety analyses including AEs and clinical laboratory data. Study treatment exposure also will be summarized using the Safety set. Efficacy analyses performed in the Safety set will be considered to be supportive.

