##### 5.1.1.1 Progression-free Survival (PFS)

PFS by investigator's review will be the primary endpoint. PFS by investigator's assessment is defined as the time from randomization to the investigator-determined (using RECIST v1.1) date of disease progression or death, whichever comes first:

[PFS = investigator-determined PD date or death date – randomization date + 1].

Investigator-determined PD event includes the followings:

- Disease progression per RECIST v1.1
- Symptomatic deterioration (global health deterioration) as described by RECIST v1.1
- For subjects with NED at time of randomization, any new malignant lesion that occurs after randomization per RECIST v1.1

PFS will be right-censored based on Table 3 for subjects who meet the following conditions:

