## 6.3 Safety Set

The Safety set consists of all subjects taking any amount of study drug. The safety set is the primary set for safety analyses including AEs and clinical laboratory data. Study treatment exposure also will be summarized using the safety set.

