### **8.2.2.2 Sensitive Analysis of Primary Endpoints (PFS/OS)**

The sensitive analyses of primary endpoints will include:

- OS using the Safety set, according to the treated arm

- PFS by investigator assessment and OS using the EE set
- PFS by investigator assessment in the ITT set, with start of subsequent anti-cancer therapy as a PFS event
- PFS based on the IRC response assessment, if required, for both ITT and EE sets as supportive analysis
- Stratified Cox proportional hazard model for PFS or OS, in ITT set, with additional covariates of number of cycles in first line chemotherapy, and/or type of prior therapy (adjuvant/neoadjuvant chemotherapy and surgery and/or radiotherapy)
- PFS and OS by Fleming-Harrington weighted log-rank test with  $\rho = 0$ ,  $\gamma = 1$ , for adjustment of delayed effects.
- The Fleming-Harrington weight for late effects is defined as below
 
$$W_n(t) = (S_n(t))^{\rho} (1 - S_n(t))^{\gamma}$$
- PFS and OS by piecewise Cox proportional model in presence of non-proportional hazard for time-varying treatment effect:
 
$$h(t | z_i) = h_o(t) \exp(\alpha z_{1i} + \beta_1 z_{2i} 1(t \leq c_i) + \beta_2 z_{2i} 1(c_i < t \leq c_{i+1}) + \beta_3 z_{2i} 1(t > c_{i+1}))$$

Where  $Z_{1i}$  is time-independent covariates such as stratification factors;  $C_i$  and  $C_{i+1}$  are cut points (e.g. 4 and 8 months, respectively) for time period and  $I(\cdot)$  denotes the indicator function.
- PFS and OS not censoring events that occur after the cutoff.
- OS with competing events being taken into consideration. Competing events for death are “definite” lost to follow-up and withdrawal of consent for continued survival assessments. Both of these competing events are subject to revision for an individual subject with the passage of time. The cumulative incidence estimates will be plotted if the percent of subjects with competing events in either arm exceeds 3%.
- PFS with competing events being taken into consideration. Competing events for PFS event are lost to follow-up, withdrawal of consent, start of other anti-cancer therapy, or two or more missing scans prior to a PFS event. The cumulative incidence estimates will be plotted if the percent of subjects with competing events in either arm exceeds 3%.

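### The EE set requires a post-baseline scan, so treated subjects who die, or deteriorate and are never scanned, in the first 8 weeks or so drop out of the EE analyses of OS, PFS and ORR

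*SAP*

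**What the plan says.** SAP 6.2 leaves out anyone with a major violation of the protocol and limits the EE set to those "who have received at least 1 dose of study treatment, and have the baseline and at least 1 post-baseline tumor assessments available". Protocol 7.2 has the same condition: subjects must "have the baseline and at least 1 post-baseline tumor assessments available". Neither document provides for a subject who dies or deteriorates before that assessment. SAP 6.2 gives the set its role: "Efficacy analyses performed in the EE set will be considered to be supportive".

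SAP 8.2.2.2 includes "PFS by investigator assessment and OS using the EE set" among the sensitivity analyses of the primary endpoints, and SAP 8.2.3.3 also estimates ORR in the EE set. OS and PFS are both timed from randomization (SAP 5.1.1). Death is an event for both. Investigator-determined progression also includes "Symptomatic deterioration (global health deterioration) as described by RECIST v1.1".

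Imaging is due at 8-week intervals after Day 1 (SAP Table 2, footnote l), and the table marks the first scan at the Day 64 visit, with a window of 3 days either way.

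Two other sets matter here. For ITT: "Efficacy analyses performed in the ITT set will be considered to be the primary indicator of efficacy". The sensitivity list also contains "OS using the Safety set, according to the treated arm", and that set needs no scan: "The Safety set consists of all subjects taking any amount of study drug".

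**The concern.** The clock starts at randomization, but entry to the EE set is decided at the first scan some 8 weeks later. A treated subject who dies in between has had an OS and PFS event and is deleted because of it. Everyone who remains was bound to survive that interval. Symptomatic deterioration is exposed in the same way: protocol 6.3.1.3 describes it as the case where radiographic evidence of progression cannot be provided, so some of these subjects will have no scan after baseline.

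A supportive analysis is there to test whether the ITT result is robust. One that conditions on early survival overstates survival in both arms, and it leaves early failures out of the ORR denominator. It also discards the period in which a vaccine would be expected to show least benefit. Protocol 1.1.1 expects immune responses mainly in the third month, and SAP 8.2.2.2 plans a weighted log-rank test and a piecewise Cox model for delayed or time-varying effects. Agreement between EE and ITT could then reassure more than it should. For PFS, EE is the only alternative population listed, since there is no Safety-set PFS analysis.

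**Working it through.** **Inputs.** From SAP 4: placebo median OS 20 months, HR 0.59, 124 subjects per arm, one-sided alpha 0.0125, power 90%, 179 deaths, and accrual over 24 months (25% in the first year, 75% in the second). From SAP 7.1: 1 month = 30.4375 days. First scan: 56 to 66 days after Day 1, from the 8-week interval up to the late edge of the Day 64 window. Assumed: exponential survival, no dropout, and scans on schedule.

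**The plan's own figure.** Required deaths = 4(z₀.₉₈₇₅ + z₀.₉₀)² / (ln 0.59)² = 4(2.2414 + 1.2816)² / 0.2784 ≈ 178.3, rounded up to 179. This matches the plan. The accrual model gives 182.3 deaths by month 66 and reaches 179 at about month 64. There is no sample-size error.

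**Deaths before the first scan.** P(death by t) = 1 − 2^(−t/20) on placebo and 1 − 2^(−0.59t/20) on CMB305.

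| First scan (days) | t (months) | Placebo | CMB305 | Total | Share of 179 |
|---|---|---|---|---|---|
| 56 | 1.84 | 6.2% → 7.7 | 3.7% → 4.6 | 12.2 | 6.8% |
| 63 | 2.07 | 6.9% → 8.6 | 4.1% → 5.1 | 13.7 | 7.7% |
| 66 | 2.17 | 7.2% → 9.0 | 4.3% → 5.4 | 14.4 | 8.0% |

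If the true HR were 1, the total would be 15 to 18.

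**EE survival levels.** Conditional on surviving to t, the EE curve is S(m − t) in place of S(m), so each median moves up by t. The placebo median goes from 20 to 21.8–22.2 months and the CMB305 median from 33.9 to 35.7–36.1 months. With a 56-day scan, the OS rates that the SAP will report change as follows.

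| Month | Placebo, all → EE | CMB305, all → EE |
|---|---|---|
| 12 | 66.0% → 70.3% | 78.2% → 81.2% |
| 18 | 53.6% → 57.1% | 69.2% → 71.9% |
| 24 | 43.5% → 46.4% | 61.2% → 63.6% |
| 30 | 35.4% → 37.7% | 54.2% → 56.2% |

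**Hazard ratio.** For each scenario, 3,000 trials of 248 subjects were simulated, cut at the 179th death and fitted with an unstratified Cox model. The EE set was represented by subjects who survived past day 56. The early HRs are illustrative and are not taken from the documents.

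| HR to day 56, then after | Deaths removed, placebo / CMB305 | ITT HR | EE HR |
|---|---|---|---|
| 0.59, 0.59 | 7.8 / 4.6 | 0.588 | 0.588 |
| 1, 0.59 (delayed effect) | 7.7 / 7.6 | 0.616 | 0.589 |
| 2, 0.59 (early harm) | 7.6 / 14.9 | 0.688 | 0.589 |
| 2, 1 (early harm, no benefit) | 7.6 / 14.8 | 1.086 | 0.997 |

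In every row the EE analysis returns the later HR, whatever happened before the first scan.

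**PFS and ORR.** RECIST progression found at the first scan is kept. What PFS loses is the early deaths above plus symptomatic deteriorations that are never scanned. The documents give no rate for the latter, so that part cannot be sized. For ORR, the same subjects leave the EE denominator.

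**The case against.** The case for leaving the plan alone is that EE decides nothing. Success is tested in ITT, the alpha allocation in SAP 7.3 gives EE no role, and under the plan's own proportional-hazards assumption the EE hazard ratio is the same as in ITT. All of this stands, and it limits the point to a supportive analysis.

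A reader might infer four stronger things that the documents do not support.

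- *All supportive OS and PFS analyses lose these subjects.* They do not. Safety-set OS needs only a dose, and the ITT PFS sensitivity analyses use everyone randomized.
- *Every early symptomatic deterioration is removed.* Protocol 6.5 asks for all efforts to continue tumor assessments, and 6.5.2 keeps subjects in imaging after several kinds of treatment discontinuation. A subject scanned later meets the EE rule.
- *Early harm would be hidden from the trial.* It would be absent from the EE comparison only. ITT keeps the deaths, SAP 8.3.1 tabulates fatal TEAEs, SAP 8.1.1 tabulates exclusions from each set with reasons, and the DMC reviews safety data.
- *The EE hazard ratio is always biased.* It is biased only if the early and later effects differ.

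The size can also be challenged. A constant hazard from Day 1 probably overstates early deaths, because protocol 4.2 requires a life expectancy of at least 6 months, ECOG 0 or 1 and no progression. That is fair, and 12 to 14 is best read as an upper-range figure.

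None of this removes the defect. The written rule still selects on survival after time zero, and the delayed-effect case that tilts the EE estimate toward CMB305 is one the SAP itself plans for.

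**Conclusion.** The point holds for the EE analyses of OS, PFS and ORR, and only for those. At the plan's OS assumptions about 12 to 14 deaths are removed, probably an upper-range count, and EE survival rates and medians are inflated, the medians by about 2 months per arm. The EE hazard ratio is unbiased under proportional hazards, moves from 0.62 to 0.59 in CMB305's favor under a delayed effect, and cannot register harm confined to the first 8 weeks.

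These figures rest on exponential survival, no dropout, on-schedule scans and, for the non-proportional cases, assumed early HRs. The primary inference is sound. The change is worth making because a planned robustness check is biased by construction and is cheap to repair before database lock.

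**What to change.** 1. In SAP 6.2 and protocol 7.2, replace the tumor-assessment condition with: *a baseline tumor assessment and at least 1 post-baseline tumor assessment, or death or documented symptomatic deterioration before the first post-baseline assessment*. At minimum, do not use the EE set for OS.
2. Clarify the last row of SAP Table 3. It can be read as censoring at randomization a subject with symptomatic deterioration and no adequate post-baseline scan, which would conflict with the PFS event list in SAP 5.1.1.1. State that symptomatic deterioration or death without an adequate post-baseline scan is a PFS event. Without this, the EE clause alone would not guarantee that these subjects contribute an event.
3. State in SAP 8.2.3.3 that these subjects count as non-responders for EE ORR.

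The cost is one clause in each document, one clarified table row and one sentence on ORR. No new data are needed.

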## 6.3 Safety Set

The Safety set consists of all subjects taking any amount of study drug. The safety set is the primary set for safety analyses including AEs and clinical laboratory data. Study treatment exposure also will be summarized using the safety set.

## 7 GENERAL STATISTICAL CONSIDERATIONS

### 7.1 Data Summaries and Conventions

Formal statistical tests will be performed for inference, unless otherwise specified, P-values will be reported to four (4) decimal places and those less than 0.0001 will be reported as <0.0001, 2-side 95% confidence intervals will be presented where appropriate. All analyses will be presented by treatment arm and overall.

Unless specified otherwise, all summaries will be comprised of standard descriptive statistics. Standard descriptive statistics include:

- For continuous parameters: number of observations (or subjects), mean, standard deviation, median, minimum and maximum
- For categorical parameters: frequency and percent of observations in each category

The following rules will be used for the days to months/years conversion:

- 1 month = 30.4375 days
- 1 year = 365.25 days

As appropriate, all data collected on the electronic case report form (eCRF) will be presented in data listings. All statistical analyses will be performed using SAS® version 9.4 or above.

## 7.2 Handling of Dropouts or Missing Data

In order to achieve the goal of a well-conducted clinical study according to Good Clinical Practice, every effort will be made to collect all data. However, despite best efforts, it may be inevitable that some data may be missing or incomplete.

In the subject data listing all available data, including partial data, will be presented as they are recorded on the case report forms (CRFs).

Time to event or duration of event endpoints will be calculated based on the study day of the event date (or censoring date) rather than visit number or visit label. Missing efficacy or safety data will not be imputed unless otherwise specified.

### 7.2.1 Partial Dates for Adverse Events

For adverse events (AEs) with partially missing start dates, it's necessary to impute an AE start date to define TEAE. For the partial date of AE start date (missing day and/or month and/or year), the following imputation rules will be applied:

- If year of the AE start date is missing, no date imputation will be made and the AE will not be considered treatment-emergent unless the investigator has deemed it to be treatment-related.
- If both day and month of the AE start date are missing but year is known, the day and month will be imputed with the day and month of the first study dose date if the year is equal to the year of first dose. Otherwise, the month and day is imputed as the first day of the year (01 Jan).
- If only day is missing, and if the year and month are equal to the first dose date, the day will be imputed as day of the first dose date. Otherwise, the day will be imputed as "01."

Partial AE end dates will be imputed for non-ongoing AEs as follows:

- If year of the AE end date is missing, no date imputation will be made.
- If both day and month of the AE end date are missing but year is known, the date of the last dose of study drug will be used as the end date of the AE. Otherwise, December 31 will be used as the end of the AE.
- If only day is missing, the date of last dose of study drug will be used as the end date of the AE. Otherwise, the last day of the month will be used as the end of the AE.

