6.4.7.2 Adverse Event Reporting

All SAEs that are unexpected and considered possibly, probably, or definitely related to study drug by the investigator or sponsor will be reported to the Food and Drug Administration (FDA), applicable regulatory agencies, and IRB/IEC in accordance with the requirements in 21 Code of Federal Regulations (CFR) §312.32 and International Conference on Harmonization (ICH) guidelines.

At each study visit (including unscheduled visits), the investigator, or designee, will determine whether any AEs have occurred. Each AE will be reported in the subject's medical record and on the AE eCRF page and classified according to the criteria in [Section 6.4.7.4](#), [Section 6.4.7.6](#), and [Section 6.4.7.7](#). If known, the diagnosis should be recorded, in preference to the listing of individual signs and symptoms. Any pre-existing conditions that are detected as part of the initial screening procedures will be reported in the medical history and not as an AE. However, pre-existing conditions that worsen after enrollment should be reported as an AE.

Adverse events will be reported to the FDA and applicable regulatory authorities in accordance with the requirements outlined in 21 CFR §312.32 and ICH guidelines. Progression of cancer is not considered an AE unless it is considered to be drug-related by the investigator. Deaths due to cancer progression will not be reported as expedited events. The investigator will continue to monitor the subject until any new, changed, or worsened AE resolves, returns to baseline, or until the investigator and IMDZ agree that follow-up is no longer necessary. AEs must be followed until resolution whenever possible.

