7.8 Safety Analysis

Safety will be assessed primarily based on reported AEs. A TEAE is an AE with an onset on or after the initiation of study treatment, or a pre-existing condition that worsens after initiation of study treatment (i.e., increase in severity). Medical events of interest, immune-mediated events, and AEs that occur more than 30 days after the last dose, and that are deemed as related to the study drug, will be included as TEAEs. TEAEs occurring from the time of the first dose through 30 days after the last dose of the study drug and medical events of interest, immune-mediated events and related AEs will be summarized. All AEs will be coded using the Medical Dictionary for Regulatory Affairs® (MedDRA v20.0 or newer). TEAEs will be tabulated by system organ class, preferred term, by treatment, and will be further categorized by NCI-CTCAE (v4.03 or newer) grade, and by relationship to the study drug. Clinically significant laboratory abnormalities, as measured by either the local or central laboratory, will be reported as AEs. The incidence for each AE will be provided as the total number of subjects that experience the AE, as well as the percentage of the population that this represents. If an AE is reported more than once during treatment for a given subject, the worst grade of severity and the most conservative relationship will be presented in the summary tables.

AEs will also be listed for individual subjects, along with information regarding onset, duration, grade, relationship to the study drug, and outcome. AEs that lead to withdrawal from the study treatment will be listed and summarized. Tabulations and listings of SAEs and deaths also will be generated.

Treatment exposure will be provided by treatment arm. The number of CMB305 or placebo injections, duration of exposure, and number of subjects with dose reductions/interruptions will be summarized by treatment arm based on the Safety set.

Laboratory values measured by the central laboratory will be used in the analysis of laboratory toxicities and will be defined based on universal normal ranges and NCI-CTCAE, Version 4.03 or newer. The number and percentage of subjects will be summarized by grade using the most severe grade by treatment arm. Clinically significant changes in laboratory values will be summarized by treatment arm. Laboratory values will be listed, with grade 3 or 4 values flagged.

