### 8.3.1 Adverse Events

The verbatim terms used in the eCRF by investigators to identify adverse events will be coded to a system organ class (SOC) and a preferred term (PT) using the current Medical Dictionary for Regulatory Activities (MedDRA) version 21.0 or higher. The severity of adverse events is assessed in National Cancer Institute (NCI) common toxicity criteria for adverse events (CTCAE) Version 4.03 or higher. Only TEAEs occurring from the time of the first dose through 30 days after the last dose of the study drug and medical events of interest, immune-mediated events and related AEs will be summarized, while all AEs captured in eCRF will be listed in data listings.

TEAE will be summarized by system SOC and PT, by severity, by relationship to study treatment, and by action taken. Tables will be sorted by frequency in incidence (the highest to lowest incidence in total column).

The following TEAEs will be tabulated and organized as follows:

- Overall Summary of Treatment Emergent Adverse Events
- TEAEs by system organ class and preferred term
- TEAEs by system organ class, preferred term and worst NCI CTCAE grade
- Severe TEAEs (Grade 3 or higher) by system organ class and preferred term
- SAEs by system organ class and preferred term and worst NCI CTCAE grade
- Related TEAEs by system organ class and preferred term
- Related SAEs by system organ class and preferred term
- Related TEAEs by system organ class, preferred term and worst NCI CTCAE grade
- Related SAEs by system organ class and preferred term and worst NCI CTCAE grade
- TEAEs leading to treatment discontinuation by system organ class and preferred term
- Related TEAEs leading to treatment discontinuation by system organ class and preferred term
- TEAEs classified as Medical Event of Interest (MEOI) by system organ class and preferred term
- TEAEs resulting in death by system organ class and preferred term

TEAEs will be summarized by presenting the number and percentage of subjects having at least one TEAE in each system organ class and preferred term. A subject with multiple occurrences of the same TEAE will be counted only once in the AE category.

Separate TEAE summaries will be presented by system organ class, preferred term, and maximum CTCAE (4.03 or higher) grade. A subject with multiple CTCAE grades for the same TEAE will be summarized under the maximum CTCAE grade recorded for the event.

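### An adverse event with no start year is left out of the treatment-emergent summaries unless judged related, which is the less cautious default and runs against the neighbouring date rules

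*SAP*

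**What the plan says.** SAP Section 7.2.1 gives three rules for incomplete AE start dates.

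- **Year missing:** "no date imputation will be made and the AE will not be considered treatment-emergent unless the investigator has deemed it to be treatment-related".
- **Day and month missing, year equal to the first-dose year:** "the day and month will be imputed with the day and month of the first study dose date". For any other year, onset becomes 1 January of that year.
- **Only the day missing, year and month equal to those of first dose:** "the day will be imputed as day of the first dose date". Otherwise onset becomes the first of the recorded month.

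SAP Section 5.2.1 defines a TEAE as "any AE that newly appeared or worsened in severity following initiation of the study treatment administration until 30 days after last dose" of study treatment, and then adds: "In addition, all study treatment related AEs are treated as TEAE". The protocol's definition (Section 7.8) is also based on timing: "A TEAE is an AE with an onset on or after the initiation of study treatment", or a pre-existing condition that worsens after treatment starts.

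SAP Section 8.3.1 sets what is tabulated. Besides in-window TEAEs, "medical events of interest, immune-mediated events and related AEs will be summarized, while all AEs captured in eCRF will be listed in data listings".

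**The concern.** When onset is unknown, the usual cautious choice in a safety analysis is to count the event unless something shows that it began outside the treatment window. The missing-year bullet does the opposite. It also makes inclusion depend on the investigator's causality judgement. Neither TEAE definition uses causality for events that start on treatment, so a data gap brings it in.

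An event coded unrelated could therefore be absent from the TEAE incidence tables only because a year was not recorded. Incidence tables are meant to allow a comparison of arms that does not depend on individual causality calls. The efficacy analyses and the type I error rate are not involved.

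**Working it through.** The plan gives no figure for this point, so there is none to reproduce. The check applies the rules to example records and then bounds the effect.

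**1. The three rules side by side.** Assume, for illustration, first dose on 15 November 2018 and last dose on 1 June 2019. The SAP window then runs from 15 November 2018 to 1 July 2019 (last dose plus 30 days).

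| Recorded AE start | Onset under SAP 7.2.1 | TEAE if not related | TEAE if related |
|---|---|---|---|
| Nov 2018, day missing | 15 Nov 2018 | yes | yes |
| 2018, day and month missing | 15 Nov 2018 | yes | yes |
| 2019, day and month missing | 1 Jan 2019 | yes | yes |
| Mar 2019, day missing | 1 Mar 2019 | yes | yes |
| 10 March, year missing | none | **no** | yes |
| Date wholly missing | none | **no** | yes |

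With a known year, an event is classed as starting before treatment only if the recorded part of the date places it there. With the year missing, relatedness alone decides.

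**2. What the exception for related events adds.** SAP Section 5.2.1 already makes every related AE a TEAE whatever its date. The exception changes nothing, so the bullet's whole effect is to exclude AEs coded unrelated.

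**3. Where such records probably fall in time.**
- Protocol Section 6.4.7.2: a pre-existing condition found in the initial screening procedures "will be reported in the medical history and not as an AE".
- Protocol Table 1 (Pre-screening and Screening) has no AE-reporting row. In Table 2, AE reporting starts at Day 1.
- Protocol Section 6.4.7.3: between main consent and Day 1, only SAEs and hospitalizations related to study tests or procedures are entered.
- Protocol Section 6.4.7.1: after 30 days from last dose, AEs are mainly collected if possibly related. The exceptions are medical events of interest, immune-mediated events and secondary malignancies, which are reported regardless of causality to 90 days (or to 30 days after new anti-cancer therapy, if earlier).

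An unrelated AE record with no year is therefore most likely to have started inside the window. This is an inference. Protocol Section 6.4.7 describes AE collection from enrollment, so a few records could precede dosing, and a few could follow the window.

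**4. Size for one subject.** SAP Section 8.3.1 counts subjects, once per term. With 124 planned per arm, one dropped subject changes a row by at most 1/124 = 0.8 percentage points. The change is zero if the subject has another counted event in that row. The true denominator is the Safety set, which may not equal 124.

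**5. Share of AE records.** The documents give no rate. Assume that 0.1% to 2% of AE records lack a start year and that 30% to 70% of those are judged related. The share of records excluded = missing-year rate × (1 − proportion related):
- low end: 0.001 × (1 − 0.7) = 0.0003, or 0.03%
- high end: 0.02 × (1 − 0.3) = 0.014, or 1.4%

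**6. Reversing the default.** Both missing-year, not-related entries in the table change from no to yes. No other entry changes.

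**The case against.** The best case for leaving the rule alone is that it is explicit, prespecified, identical in both blinded arms, and almost never triggered. AEs are asked about at every visit (Protocol Section 6.4.7.2). Visits are two to three weeks apart up to Day 92 and every 8 weeks during the boost phase, so the visit nearly fixes the year. Data are source-verified and queried (Section 8.11), and only complete, signed eCRFs are accepted (Section 8.16). No protocol text sets a different rule for missing dates. All of this stands, and it is why the point is minor. It does not explain why this one bullet defaults to exclusion.

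A reader might go further and infer that serious events coded unrelated could disappear from the safety report. The documents do not support that.
- All AEs are listed (SAP Section 8.3.1), with partial data shown as recorded (SAP Section 7.2).
- Protocol Section 7.8 requires tabulations and listings of SAEs and deaths, with no treatment-emergent limit.
- SAEs, grade 3 or higher events and medical events of interest must be notified within 24 hours (Protocol Section 6.4), which makes a serious event with no known year unlikely.

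Some ambiguity remains. In SAP Section 8.3.1 the SAE rows are not titled as TEAEs but sit under a lead-in that refers to TEAEs. The rows for deaths and for medical events of interest are titled as TEAEs, although the same section says that medical events of interest are summarized alongside TEAEs. This does not clearly return a missing-year event to those summaries, and it does not show that serious events are lost.

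It is also fair to object that counting every missing-year AE unless it ended before first dose would be too wide. Unrelated events starting more than 30 days after last dose would be counted, contrary to SAP Section 5.2.1. The replacement rule needs an upper bound.

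**Conclusion.** The missing-year bullet takes the non-conservative default, is out of line with its neighbours, and affects only AEs coded unrelated. The consequence is confined to the TEAE summaries.

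The size is expected to be small. The ceiling of 0.8 percentage points per dropped subject assumes that all 124 in an arm are dosed and that the subject has nothing else counted in the row. It should not be read as the effect of every dropped record. The range of 0.03% to 1.4% of AE records rests wholly on assumed rates. The conclusion about the rule's direction needs neither number: it follows from SAP Sections 7.2.1 and 5.2.1 read together. The case for changing it also rests on the inference that unrelated records without a year mostly began on treatment.

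**What to change.** Replace the missing-year start-date bullet in SAP Section 7.2.1 with wording such as:

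> An AE whose start year is missing counts as treatment-emergent unless other recorded date information shows that it began outside the treatment-emergent window (for example, an end date before first dose, or information placing onset before first dose or more than 30 days after last dose). Related AEs remain TEAEs as defined in Section 5.2.1.

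The cost is one bullet and a small change to the derivation, using data already collected. The change contradicts no protocol text. The downside is that TEAE counts may rise slightly, and an occasional event that truly began outside the window will be counted when nothing else on record dates it. The bullet should be settled before database lock.
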